In 10/2018, the study team had meetings with all willing ED clinicians at the intervention sites. At intervention site 1, these meetings were face-to-face and took place during a two-day time frame when [name], an Infectious Disease (ID) physician, was present on-site. These one-on-one meetings with each clinician lasted 10-15 minutes and included a review of the clinician's individual antimicrobial-prescribing data (see feedback metrics), an anonymous comparison to his/her local peers, and a review of antimicrobial-prescribing guidelines. At intervention site 2, [name] enrolled ED clinicians by telephone while an on-site ID physician

([name]) met with clinicians in-person. The content of these meetings was identical to those at intervention site 1.

After the initial meeting, the study team e-mailed updated data to each participating clinician on his/her antimicrobial use. These e-mails were sent once every quarter. Overall, three e-mails were sent over the 12-month study period. E-mails were not sent after the fourth quarter, as the study had concluded by that point.

Beginning in late September 2018, a clinical pharmacist was assigned to the ED at intervention site 2 from 10a-10p every day. One of the clinical pharmacist's responsibilities was to ensure adequate antimicrobial selection. These pharmacists were not part of this trial, and the study team was only made aware of their presence as the intervention period was about to begin. To account for this, separate analyses were performed for intervention sites 1 and 2.

*Feedback metrics:* Feedback at the enrollment visit and in each quarterly e-mail update consisted of two metrics: 1) the clinician's total antimicrobial-prescribing volume adjusted for the total number of ED patient-visits, i.e. a total antimicrobial prescribing rate, and 2) the clinician's rate of prescribing antibiotics for uncomplicated viral acute respiratory infections (ARI), based on data from the VA's internal Academic Detailing website. The ARI metric included visits for acute bronchitis and non-specific upper respiratory tract infections but excluded visits for patients who were immunosuppressed, had chronic lung disease, or had a concurrent infection.

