For the enrollment meeting with clinicians, both metrics were based on the year preceding the initiation of the study. Once the intervention period began, data on the clinician's total antimicrobial-prescribing rate was only drawn from the intervention period, which could include more than one quarter. Data on the ARI metric was only provided if the patient had seen  $\geq 8$  eligible ARI cases during the prior quarter; if there were not 8 eligible visits during the prior quarter, then more than one quarter of data could be included as long as the data was all from the intervention period.

At enrollment, clinicians were compared to their peers for both metrics. In subsequent e-mail communications, clinicians were compared to their peers and to their own prior performance for the ARI metric. For the total antimicrobial-prescribing rate, e-mails only compared clinicians to their personal baseline performance. The wording used in all feedback reports was based on the MITIGATE toolkit (Supplemental Table 1). All peer-to-peer comparisons were also demonstrated graphically in an attachment to the e-mail (Supplemental Figure 1).

To assess whether the clinician received the e-mail feedback, we requested a read receipt for all e-mail communication. The percentage of read receipts that were acknowledged was tracked over time.

We did not educate or provide feedback to ED clinicians at the two control sites. The control sites were not aware that their antimicrobial-prescribing was being monitored.

Outcomes: The primary outcome was the cumulative frequency of an outpatient antimicrobial prescription within 24 hours of the ED visit. ED visits that resulted in an inpatient admission within 24 hours after the visit were not eligible for inclusion in the outcome. Antimicrobials were defined as all agents included in the National Healthcare Safety Network's (NHSN) Antimicrobial Use and Resistance Module. On a monthly basis, the cumulative number of outpatient antimicrobials prescribed by the ED and the total number of eligible ED visits were used as the numerator and denominator, respectively. This outcome was chosen as it would not be influenced by diagnostic shifting.

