The secondary outcome was the proportion of ED visits associated with an outpatient antibiotic prescription within 24 hours of the ED visit; it was calculated similar to antimicrobial use. Antibiotics were defined as all antibacterial agents, as defined by the NHSN's Antimicrobial Use and Resistance Module.

The ARI metric, as defined above, was captured across all clinicians at the control and intervention sites. Guideline-concordant management was assessed using manual chart

reviews (see below). Other secondary outcomes were measured from 24 hours after the ED visit up to 30 days after the visit. These secondary outcomes included testing for the presence of *Clostridioides difficile*, confirmed *C. difficile* infection (CDI), return ED visit, late antimicrobial use, late antibiotic use, and admission to a VHA acute-care facility. CDI linked to a visit was confirmed if the patient had a positive *C. difficile* test and a qualifying antibiotic (metronidazole, oral vancomycin, or fidaxomicin) was dispensed to the patient within 7 days of the positive *C. difficile* test. Visits that occurred from 24 hours up to 30 days after the prior visit were recorded as a return ED visit. ED visits that occurred after 30 days from the prior ED visit were considered as independent visits. Primary and secondary outcomes, except return ED visits, included all eligible visits in the denominator.

Data on oral antimicrobial prescriptions, demographics, comorbidities, infections, and laboratory data for *Clostridioides difficile* for ED visits during the study period were extracted from the Corporate Data Warehouse (CDW) using the VA Informatics and Computing Infrastructure (VINCI). The *International Classification of Diseases*, Tenth Revision (ICD-10) codes were used to identify existing comorbidities and infection diagnoses linked to the ED visit.

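### The ARI prescribing rate is both a feedback target at the intervention EDs and an outcome at all four EDs, and no planned check separates fewer antibiotics from changed diagnosis coding

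*Combined protocol and SAP*

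**What the plan says.** All of the text is in METHODS of the combined protocol and SAP.

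- **Feedback metrics.** The second of the two metrics is "the clinician's rate of prescribing antibiotics for uncomplicated viral acute respiratory infections (ARI), based on data from the VA's internal Academic Detailing website". On the denominator: "The ARI metric included visits for acute bronchitis and non-specific upper respiratory tract infections". Visits were dropped if the patient was immunosuppressed, "had chronic lung disease, or had a concurrent infection".
- **Use of the metric in feedback.** Peers were the comparator for both metrics at enrollment. In the later e-mails "clinicians were compared to their peers and to their own prior performance for the ARI metric", while total prescribing was set only against the clinician's own baseline. Control EDs received no feedback and did not know they were being monitored.
- **Outcomes.** "The ARI metric, as defined above, was captured across all clinicians at the control and intervention sites". This sentence follows the all-visit antibiotic outcome, and the text soon goes on: "Other secondary outcomes were measured from 24 hours after the ED visit up to 30 days after the visit". The metric is therefore a secondary outcome by placement; it is never labelled as one.
- **Diagnostic shifting.** The plan names this threat when it justifies the primary outcome: "This outcome was chosen as it would not be influenced by diagnostic shifting".
- **Diagnosis data.** In the study's own data extract, ICD-10 "codes were used to identify existing comorbidities and infection diagnoses linked to the ED visit".
- **Statistical Analysis.** Secondary outcomes are modelled by Poisson regression, with an interaction of study period and site type giving the incidence rate ratio (IRR).

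**The concern.** A rate over all ED visits cannot be changed by relabelling a visit. A rate over bronchitis and URI visits can. If a treated visit is recorded as sinusitis or pneumonia, or with an added concurrent infection or chronic lung disease, it leaves both numerator and denominator, and the rate falls although the prescription was written.

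The control group does not remove this. The motive to code differently comes from the feedback, which only the intervention EDs received, and peer comparison continued in the e-mails for this metric alone. Any resulting artefact would go into the period-by-site interaction, which is the effect estimate.

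The plan knows of the threat and avoids it in its all-visit outcomes, but it describes no safeguard for the ARI outcome. It has no analysis of how many visits are coded as ARI, of neighbouring codes, or of a broader respiratory denominator. At stake is whether an ARI reduction can be read as fewer antibiotics for viral illness.

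**Working it through.** The plan gives no baseline ARI rate, target effect or power for this metric, so there is no figure to reproduce. The calculation asks how large an artefact could be when prescribing does not change.

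**Inputs (all assumed)**
- p, the share of ARI visits treated with an antibiotic: 0.50 or 0.60, with 0.30 and 0.70 as a wider range.
- s, the share of treated ARI visits coded out of the metric at the intervention EDs, averaged over all clinicians there: 0.10 or 0.25.
- No recoding at the control EDs.

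**Formula.** Observed rate = p(1 − s)/(1 − ps). Spurious IRR = (1 − s)/(1 − ps).

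**Per 1,000 ARI visits**

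| p | s | Treated visits leaving | Observed rate | Spurious IRR | Relative change |
|---|---|---|---|---|---|
| 0.60 | 0.10 | 60 | 540/940 = 57.4% | 0.90/0.94 = 0.957 | −4% |
| 0.60 | 0.25 | 150 | 450/850 = 52.9% | 0.75/0.85 = 0.882 | −12% |
| 0.50 | 0.10 | 50 | 450/950 = 47.4% | 0.90/0.95 = 0.947 | −5% |
| 0.50 | 0.25 | 125 | 375/875 = 42.9% | 0.75/0.875 = 0.857 | −14% |

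The same 600 or 500 prescriptions are written in every row.

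**Sensitivity to p.** At s = 0.20 the spurious IRR is 0.85 for p = 0.30 and 0.93 for p = 0.70. The artefact is larger where fewer visits are treated.

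**Direction**
- *Untreated visits coded out.* If 20% of them leave, the ratio is 1/(1 − 0.2(1 − p)) = 1.16, 1.11 and 1.06 at p = 0.30, 0.50 and 0.70. The rate rises.
- *Untreated visits coded in.* If they add 10% to the denominator, the ratio is 1/1.10 = 0.91 at any p.
- A spurious reduction therefore needs mainly treated visits to leave or untreated visits to enter. That is the direction the feedback rewards.

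**Denominator wording.** Outcomes are said to use all eligible visits. If that meant all eligible ED visits for the ARI metric too, the spurious IRR would be 1 − s, that is 0.90 at s = 0.10 and 0.75 at s = 0.25. The artefact would remain, and would be larger.

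**What a check could see.** Coding treated visits out lowers the ARI-coded count by ps: 5% (0.50 × 0.10) to 15% (0.60 × 0.25) in the table. Coding untreated visits in raises the count. If the moves stay among respiratory codes, the prescribing rate over all respiratory-infection visits does not change.

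**The case against.** **The chart review already looks at diagnosis.** This is partly right. Two blinded chart reviewers judge the accuracy of the diagnosis and can reclassify it. The sampled codes include acute sinusitis, pharyngitis and AE-COPD as well as bronchitis and URI, so shifts among these can be found. But the review serves guideline-concordant management and does not correct the ARI metric. It takes only a patient's first ED visit, and its goal of at least 110 charts per site and period covers six diagnoses including cystitis. The sample is drawn by ICD-10 code, and pneumonia and other unlisted codes are outside it.

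**The all-visit outcomes give context.** They do: neither the primary outcome nor the all-visit antibiotic outcome can be moved by recoding. They cannot settle the ARI question, though. ARI visits are a subset of ED visits, so an unchanged all-visit rate fits either a real ARI reduction or a coding shift.

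**Exposure is limited.** This stands. Three e-mails went out, to participating clinicians only, and ARI data were given only once at least 8 eligible visits had accumulated. The outcome covers all clinicians, so non-participants dilute any artefact. At 10% recoding the artefact is only 4 to 5%; the 12 to 14% figures need a quarter of treated visits recoded across the intervention EDs.

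**Clinician coding is inferred.** This also stands. The metric comes from the Academic Detailing website, whose coding rule is not given. ICD-10 coding is stated for the study's extract and the chart-review sample.

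A reader might infer that clinicians were ranked on the metric. The text says only that they were compared; the report wording is in a supplement that is not among the documents.

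**Conclusion.** The point holds as a conditional risk to one secondary outcome. If feedback moves mainly treated visits out of the ARI group, or untreated visits into it, at the intervention EDs, the analysis would report a reduction with no prescription avoided. The size is about 4 to 14% relative, on the assumptions of 50 to 60% treated, 10 to 25% of treated visits recoded, and no recoding at the control EDs. It also rests on the inferences that the metric follows clinicians' coding and that, as a secondary outcome by placement, it is analysed with the period-by-site model.

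Two stronger readings are not supported. A reader might infer that recoding took place, or that any ARI reduction is an artefact; the documents contain no evidence of recoding, and recoding in the other direction would hide a benefit. A reader might also infer that the main conclusion is at risk; the primary and all-visit antibiotic outcomes are unaffected. The change is desirable and inexpensive, not essential.

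**What to change.** Keep the ARI metric as feedback and as an outcome, and state explicitly that it is secondary, what its denominator is and which diagnosis codes define it. Add two analyses from the ICD-10 diagnoses already extracted:

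1. **Coding check.** Report ARI-coded visits per total eligible ED visits, and as a share of all respiratory-infection-coded visits, by site and period. Fit the same period-by-site interaction and give its 95% CI. Show intervention sites 1 and 2 separately, as the plan already does for other reasons.
2. **Sensitivity analysis.** Repeat the antibiotic prescribing analysis over all respiratory-infection-coded visits, adding sinusitis, pharyngitis, AE-COPD and pneumonia to bronchitis and URI.

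If the ARI share falls at the intervention EDs relative to the control EDs, or the broader analysis does not support the reduction, report the ARI result as possibly due to diagnostic shifting. Read it alongside the all-visit outcomes and the chart review. A relative rise in the share together with a lower ARI rate deserves the same caution, because untreated visits may have been coded in. A change in share is not proof, since case mix or more accurate diagnosis can cause it. With four EDs, a wide interval does not rule shifting out.

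The cost is a wider code list and two more model fits, with no new chart review. The team should confirm that the extract holds pneumonia codes. The broader denominator includes visits where antibiotics are indicated, which dilutes any true effect; it therefore supplements the ARI result and does not replace it.

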## METHODS

Study design: We performed a quasi-experimental pilot study with an interrupted time-series design and a matched-pair non-equivalent control group to evaluate the effect of a pilot intervention on clinicians at 2 participating EDs versus 2 control EDs. All EDs were affiliated with Veterans Affairs Medical Centers (VAMCs) in the midwestern United States.

Ethics approval: The clinical trial was registered on ClinicalTrials.gov, NCT03349567. The Institutional Review Boards (IRB) at the University of Iowa and Indiana University as well as the

Research & Development Committee of the Iowa City and Indianapolis VAMCs approved this study and waived written informed consent. All other sites were not engaged in research activities, so local IRB approval was not sought.

Site selection: First, we contacted VAMCs within two midwestern Veterans Integrated Service Networks (VISNs) to assess their interest in participating in this study. These 2 VISNs were chosen because they were among the few VISNs that had not implemented regional initiatives to improve antimicrobial use in ambulatory care.

Once two intervention sites were identified, we pulled a year of antimicrobial-prescribing data for all EDs within these same two midwestern VISNs. Eligible control sites had a baseline antimicrobial-prescribing rate (outpatient antimicrobial prescriptions dispensed per total ED patient-visits) that was similar to the intervention sites. Selection of controls on the pre-intervention outcome of interest minimized bias and reduced the impact of regression to the mean, which is a key threat when selecting poor performers in non-randomized trials. To further ensure that intervention and control sites were as similar as possible, control and intervention sites were also matched on their hospital complexity level, as defined by the VHA.

Intervention: The entire study period was 2-years in duration. The baseline period covered 1-year between 10/01/2017 through 09/30/2018, the implementation phase lasted one month (10/2018), and the intervention period spanned another 11 months, 11/01/2018 through 09/30/2019.

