**Statistical Analysis:** An interrupted times series analysis was used to evaluate the effect of audit-and-feedback between the intervention and control sites. The crude differences in patient characteristics from baseline to intervention periods were assessed for intervention and control sites using Fisher's exact test and Wilcoxon rank-sum test. Monthly proportions of antimicrobial and antibiotic use were calculated at each site for the baseline and intervention time periods. Segmented regression analysis was conducted using generalized linear models to estimate change in monthly antimicrobial and antibiotic prescription rates between baseline and intervention periods for intervention and control sites, respectively. Models were adjusted for continuous variables for time (months before, during, and after implementation). The estimate for time during implementation was used to calculate the immediate change in prescription rates and was reported as incident rate ratios (IRR) with 95% confidence intervals (CI). Indicator

variables for the four seasons were also included in each model to adjust for seasonal trends. An R-side random statement was included in each model to vary the degree of overdispersion for each facility. Finally, a difference-in-difference estimate was reported for the change in monthly prescription rates between intervention and control sites in the intervention period while controlling for changes in the baseline period. A Poisson regression model with log link was used to estimate the rate of secondary outcomes. Models were adjusted for time as a continuous covariate, an indicator for month of implementation of intervention (October 2018), and included random effects to account for repeated measures among sites each month during the study period. An interaction variable for the study period (baseline or intervention) and site (intervention or control) was included in the model to estimate the IRR and 95% CIs.

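### The segmented models list facility-specific overdispersion but no facility intercept, so a level gap between two EDs in one model costs precision and can shift most of the weight to one ED

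*Combined protocol and SAP*

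**What the plan says.** METHODS, Study design, describes an "interrupted time-series design and a matched-pair non-equivalent control group". Under Site selection, "Eligible control sites had a baseline antimicrobial-prescribing rate" similar to that of the intervention sites, and "control and intervention sites were also matched on their hospital complexity level". The matching runs from control ED to intervention ED. Nothing matches the two EDs of one arm to each other.

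METHODS, Statistical Analysis, fits segmented generalized linear models for the intervention and the control sites. On the mean model it says: "Models were adjusted for continuous variables for time (months before, during, and after implementation", and it adds season indicators. On the variance it says: "An R-side random statement was included in each model to vary the degree of overdispersion for each facility". A difference-in-difference between arms follows. No facility or pair intercept is listed for these models, and the pairs are not mentioned again. For the Poisson models of the secondary outcomes, by contrast, the same section does state random effects for sites.

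Under Intervention, because a pharmacist was placed in the ED at intervention site 2, "separate analyses were performed for intervention sites 1 and 2". The text does not say which control ED or EDs those analyses use.

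**The concern.** The R-side term changes the variance, not the mean. If two EDs share a model with no facility intercept, both are fitted to one common level, and any lasting difference in their prescribing rates becomes residual. A common dispersion would spread that residual over both EDs. With a separate dispersion for each, the fit can improve by following one ED closely and giving the other a large dispersion, and so little weight.

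Two things are then at stake: precision, because a stable and removable difference is treated as noise; and meaning, because a pooled step may describe mainly one ED without the reader knowing which. The second matters most if the two EDs change by different amounts, which the pharmacist at site 2 makes plausible.

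**Working it through.** **Inputs.** From the documents: two EDs per arm; 12 + 1 + 11 = 24 monthly points per ED; the terms listed above. The documents give no visit counts, site rates, dispersion or within-arm gap, and no figure of their own on this point to reproduce. Assumed instead: 750-1,500 eligible visits per ED per month, rates of 15-20%, true dispersion φ from 0.85 (plain binomial variation, 1 − 0.15) to 5, and true step IRRs of 0.80 v 1.00 or 0.90 v 1.00.

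**1. Dispersion sets weight.** With expected count C, ED 1's share of the weight is (C1/φ1) / (C1/φ1 + C2/φ2). With equal counts, fitted φ ratios of 1, 3, 5 and 10 give 50%, 75%, 83% and 91%.

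**2. A level gap alone can create the ratio.** Take two EDs with equal counts, equal true steps, residual SD s on the log scale and log level gap d. If the common level lies a distance x from the midpoint, the fitted variances are s² + (d/2 − x)² and s² + (d/2 + x)². The fit minimises their product, (s² + d²/4 + x²)² − d²x².

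- For d ≤ 2s the minimum is at the midpoint, so weights are equal.
- For d > 2s it is at x² = d²/4 − s², and the followed ED's share is 1/2 + √(1/4 − s²/d²).
- Following one ED exactly beats the midpoint once d > √8·s = 2.83s.

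With 1,500 visits at 15%, the count is 225 and s = √(φ/225). The larger share is then:

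| φ | s | 10% gap (d = 0.095) | 20% gap (d = 0.182) | 30% gap (d = 0.262) |
|---|---|---|---|---|
| 0.85 | 0.061 | 0.50 | 0.87 | 0.94 |
| 1.5 | 0.082 | 0.50 | 0.72 | 0.89 |
| 3 | 0.115 | 0.50 | 0.50 | 0.74 |
| 5 | 0.149 | 0.50 | 0.50 | 0.50 |

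This is a large-sample approximation. Chance differences and unequal true steps raise the shares in finite data.

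**3. Simulation of the model as listed.** 24 months, two EDs, step coded from October 2018, true φ 1.5 in both EDs, true step IRR 0.80 v 1.00. Share of data sets in which one ED holds over 90% of the weight:

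| Baseline rates | 1,000 v 1,000 visits | 1,500 v 750 visits |
|---|---|---|
| 15% v 15% | 3% | 17% |
| 15% v 16.5% | 22% | 61% |
| 15% v 18% | 83% | 96% |
| 15% v 20% | 100% | 100% |

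In the equal-visit runs the median fitted φ ratio at the three non-zero gaps is 4.8, 10.6 and 22.9, although the true ratio is 1. At 15% v 18%, 10.6/11.6 = 0.91, which matches ED 1's median share of 0.91. Its 5th-95th percentile range is 0.06-0.96, so the dominant ED can change from one data set to the next. These runs combine the level gap with unequal steps: after the step, 15% × 0.80 = 12% faces 18%, a ratio of 1.5. They therefore overstate what a 20% gap does alone.

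**4. Dependence on φ.** At a 20% gap, 1,500 visits and true changes of −10% and 0, one ED exceeds 90% of the weight in 98% of data sets at φ 0.85, 63% at 1.5, 15% at 3 and 3% at 5.

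**5. It is the combination that matters.** With a common φ and no facility term, the share stays at the visit split (0.50 or 0.67). With facility-specific φ and a facility intercept, the 83% at 15% v 18% falls to 1%, and ED 1's median share falls from 0.91 to 0.38.

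**6. Effect on the estimate.** Across 1,000 visits, φ 1-3 and gaps of 20-33%, the intercept lowers the SD of the step by about 11-23%. In step 3's 15% v 18% case with equal visits, the mean pooled IRR is 0.88 without the intercept and 0.92 with it. The equal-weight value is √(0.80 × 1.00) = 0.894. In another setting, with changes of −10% and 0, omitting the intercept moved the pooled log step towards zero, from −0.045 to between −0.014 and −0.033.

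**The case against.** **The term list may be incomplete.** The difference-in-difference needs an arm term that is not listed either, so an unlisted facility term may also have been fitted. This stands: a reader might infer that the fitted model lacked a facility intercept, and the text does not prove it. Still, site effects are stated for the secondary-outcome models and not for these, and varying dispersion by facility in each model implies more than one facility per model.

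**The grouping is not stated.** If a model holds one intervention ED and its matched control, an arm term is a facility term and the problem disappears. This also stands. Pooling by arm is the natural reading of the section, but no pooled step is named as the primary estimate.

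**The site difference is already handled.** The separate analyses were introduced because of the pharmacist. A model with one intervention ED cannot have its intervention step taken over by the other. That limits the harm on the intervention side. It does not protect a pooled control step or a pooled difference-in-difference.

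**Inference is affected little.** Coverage stayed at roughly 90-97% in most settings. With equal true steps there was no bias, only lost precision. Coverage of the equal-weight average fell clearly, to 82%, only with near-zero overdispersion, a 20% gap and unequal steps. The direction of any drift depends on the scenario. This stands against any claim of invalid intervals or of bias in a known direction.

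**The intercept is not a full cure.** It leaves ordinary precision weighting. With 2:1 visits and 3:1 true φ, one ED still exceeds 90% of the weight in 13-22% of data sets. That is why results for each ED are needed as well.

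**Conclusion.** The concern holds as a conditional weakness of the specification. Fitted as listed, a model with two EDs absorbs their level gap into the dispersion, loses precision, and may give most of the weight to one ED. This is rare when levels are equal (0-6% of data sets above 90% weight with 1,000 visits per ED, more with unequal visits) and common when the gap is about 20% or more and overdispersion is low. At φ of 3-5 a 20% gap does much less.

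A reader might go further and conclude that the reported effect is driven almost wholly by one ED. The documents do not support that: they give no within-arm gap, visit counts or dispersion, do not state which EDs each model holds, and provide for separate site analyses. All sizes above rest on assumed values and on an approximation to the fitting software. The case for acting does not depend on the extreme settings, since the remedy gains precision at almost no cost.

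**What to change.** - Add a facility fixed effect to every segmented model that holds more than one ED, and write out the full model, including the arm terms used for the difference-in-difference. If such an effect was already fitted, say so.
- State which EDs each model holds, and which control ED or EDs each analysis of site 1 and of site 2 uses.
- Report each ED's step and fitted dispersion beside any pooled estimate, so that the weighting can be seen.
- A difference-in-difference within each matched pair may be given as a supporting analysis. It is one option for using the pairing and is not needed to stop the shift in weight.

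The cost is one parameter per additional ED, a few lines of text, and no new data.

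### The scale of the only between-arm estimate for the primary outcome is undefined and reads most naturally as a trend difference, and no between-arm contrast of the immediate change is named

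*Combined protocol and SAP*

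**What the plan says.** All of this is in the combined protocol and SAP, METHODS, Statistical Analysis, unless noted.

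- The segmented model is fitted "to estimate change in monthly antimicrobial and antibiotic prescription rates between baseline and intervention periods". The results are given for intervention and control sites "respectively" in the sense of one set per group: "between baseline and intervention periods for intervention and control sites, respectively".
- The time terms are described in one sentence: "Models were adjusted for continuous variables for time (months before, during, and after implementation". Season indicators and a facility-level overdispersion term are added.
- The middle time term supplies the step: "The estimate for time during implementation was used to calculate the immediate change in prescription rates and was reported as incident rate ratios (IRR". The sentence adds 95% CIs. It does not compare the step between arms.
- One between-arm estimate is then named: "a difference-in-difference estimate was reported for the change in monthly prescription rates between intervention and control sites in the intervention period". It is taken "while controlling for changes in the baseline period". The text does not say whether it is a ratio of slopes, of steps or of mean levels.
- A study-period by site interaction, which is a level contrast, appears only in the description of the Poisson model for secondary outcomes.
- On the exposure (METHODS, Intervention): "In 10/2018, the study team had meetings with all willing ED clinicians at the intervention sites". Three quarterly e-mails with updated data followed. Intervention sites 1 and 2 are also analysed separately because of a pharmacist newly assigned to site 2.

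**The concern.** With two non-randomised EDs per arm, the control group is the main protection against secular change in prescribing. It protects only the quantity that is actually contrasted between arms.

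The wording points to the trend as that quantity. All listed time terms are continuous. The middle one is already used for the immediate change, which leaves the slope after implementation for the intervention period and the slope before it for the baseline period. Netting out changes within baseline, rather than the baseline level, also suggests a trend.

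If so, the controlled estimate answers whether prescribing moved faster per month in one arm than in the other. It does not answer whether prescribing was lower. Much of the exposure came at the start, so an early drop that holds or wears off is a plausible pattern, and it is the one that a slope contrast misses or reverses. The reader would then have to judge the drop from two within-arm IRRs, and no named estimate would give the controlled reduction over November 2018 to September 2019.

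**Working it through.** The plan gives no visit volume, baseline rate, target effect or power for this outcome, so there is no stated figure to reproduce. The following is an illustration.

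**Inputs from the plan.** 4 EDs (2 + 2); 12 baseline months (1 to 12), October 2018 (month 13) and 11 intervention months (14 to 24); log link; season indicators.

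**Assumed, not in the plan.** 1,200 eligible visits per ED-month, 18% prescribing, Poisson variance unless stated.

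**Model, for each arm.** log rate = a + b·t + October term + S·[t ≥ 14] + d·(t − 14)·[t ≥ 14] + season.

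**Contrasts (intervention minus control, exponentiated).**
- Step ratio: exp(ΔS).
- Slope DiD: exp(Δd), per month.
- Averaged level ratio: exp(ΔS + 5·Δd), because the mean of t − 14 over months 14 to 24 is (0 + 10)/2 = 5.

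**Expected values under three effect shapes.**

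| Shape | ΔS | Δd | Step | Slope DiD | Averaged level |
|---|---|---|---|---|---|
| Sustained 10% drop | ln 0.90 = −0.105 | 0 | 0.90 | 1.000 | 0.90 |
| Drop to 0.85 fading to 1.00 | ln 0.85 = −0.1625 | 0.1625/10 = 0.01625 | 0.85 | 1.016 | exp(−0.1625 + 0.0813) = 0.922 |
| Growing from 1.00 to 0.85 | 0 | −0.01625 | 1.00 | 0.984 | exp(−0.0813) = 0.922 |

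The fade and the growth are linear on the log scale here. With a fade linear on the rate scale, the averaged ratio is 0.924.

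**How often the fading case is declared an increase by the slope DiD.** The standard error of Δd is about 0.0087 to 0.0089; take 0.0089. Probability = Φ(z − 1.96).
- Dispersion 1: z = 0.01625/0.0089 = 1.83; Φ(−0.13) ≈ 45%.
- Dispersion 2: z = 1.83/√2 = 1.29; Φ(−0.67) ≈ 25%.
- Dispersion 3: z = 1.83/√3 = 1.05; Φ(−0.91) ≈ 18%.

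For the sustained drop, the slope DiD declares a reduction only at its one-sided error rate of 2.5%.

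**Second set of assumptions, by simulation (1,000 runs each).** A 15% drop, with 1,000 visits at 12% or 2,000 visits at 15%.
- Sustained: slope DiD 1.000, with a reduction declared in 2.9% and 2.0% of runs. The step contrast is significant in 55% and 90%, and a period-by-arm level contrast in 98% and 100%.
- Fading to no effect by month 24: slope DiD 1.015, with an increase declared in 27% and 55%. The level ratio is 0.929, and no run shows a significant increase.
- Growing: slope DiD 0.985, with a reduction declared in 29% and 54%. The step ratio is 1.00.

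**Precision of the averaged contrast.** Under the 1,200-visit assumptions its log-scale standard error is 0.077 with season terms shared between arms and 0.088 with arm-specific terms. For a 10% drop, 0.105/0.077 = 1.37 and 0.105/0.088 = 1.20, so power is Φ(−0.59) ≈ 28% and Φ(−0.76) ≈ 22%. The wider of the two 95% CIs around 0.90 is 0.90·exp(±1.96 × 0.088), or 0.76 to 1.07. The 0.088 assumes seasons cut at December, March, June and September. The plan does not define its four seasons, and arm-specific terms on quarters starting in October would widen the interval considerably.

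**The case against.** The strongest reply is that the plan never says slope or trend. The outcome is itself a monthly rate, so a change in monthly rates can simply mean a change in its level, and the same section uses nearly the same phrase for the change between periods. A conventional DiD is a level contrast. On that reading the harm disappears: in the second illustration the sustained and fading drops give 0.850 and 0.929, both reductions. This stands. A reader might infer that the controlled analysis is certainly blind to a step, or that the model has no level term. The documents support neither: the middle time term, if held at its value after October, acts as a level term, and giving results per arm does not exclude a joint model.

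The exposure is also not purely a one-off. Three quarterly e-mails could produce a growing effect, which the slope DiD detects in the right direction and the step contrast misses. This stands too, and it is why the step should not simply replace the slope.

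A third reply is that the within-arm steps carry 95% CIs, so with separate fits a reader could form their ratio by hand. That is correct for independent fits. It fails if the arms share terms, and the plan does not name that ratio as a result.

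Finally, this is a pilot, and the averaged contrast has low power (22% to 28% for a 10% drop). That argues against imposing it as the primary estimate, not against reporting it.

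**Conclusion.** The point holds in a conditional form. Two things follow from the text alone: the scale of the only between-arm estimate for the primary outcome is undefined, and no between-arm contrast of the immediate change is named. A trend difference is the best-supported reading of the DiD, but it is an inference.

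If that reading is right, the expected DiD is 1.00 for any sustained step. For a drop to 0.85 fading to 1.00 it is 1.016 per month although average prescribing is about 8% lower (1 − 0.922), with a wrong-direction nominal finding in about 45% of trials (18% to 25% with dispersion 3 to 2). If a level contrast was meant, these consequences do not arise and the defect is one of definition. Even then, an analyst could report a slope, a step or a level from the same data and comply with the plan.

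The percentages rest on assumed volumes, prescribing rate and dispersion. The expected ratios depend only on the assumed shape of the effect.

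**What to change.** State in Statistical Analysis the model terms, their coding and the scale of the DiD. From a model containing both arms, report with 95% CIs:

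1. the between-arm ratio of the immediate change, exp(ΔS);
2. the between-arm level ratio averaged over November 2018 to September 2019, exp(ΔS + 5·Δd);
3. the slope DiD, exp(Δd), as a description of fading or growth.

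Report the same three in the separate analyses of intervention sites 1 and 2. Add a sentence that an effect will not be inferred from comparing two within-arm IRRs.

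Which contrast is primary, and whether the arms share season terms, is the sponsor's choice and should be written down. Shared terms give more precision (a step standard error of 0.061 against 0.077 under the 1,200-visit assumptions) but assume equal seasonality.

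The cost is SAP wording and linear contrasts from a segmented model of the kind already planned. The downsides are more estimates to report and a wide interval for the averaged contrast: a log-scale standard error of about 0.08 to 0.09 before overdispersion, and larger when only one intervention ED is analysed.
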